This is a 2-arm pragmatic cluster RCT comparing an enhanced blended learning implementation package to a standard implementation package. The study will be conducted at Tingathe-supported health facilities in Machinga and Balaka, Malawi. Thirty-three clusters will be randomized in a 2:1 ratio to the standard versus enhanced packages. All clusters will receive the standard of care. Additionally, enhanced clusters will receive an enhanced blended learning training and enhanced facility support. Three sets of primary outcomes will be compared between the standard and enhanced arm: implementation outcomes, service uptake outcomes, and cost-effectiveness outcomes. The standard of care sites will receive the enhanced implementation package after the primary observation period ends. Long-term outcomes will be examined at all clusters. Prior to the trial, the enhanced implementation package and all study tools will be pilot tested for feasibility and acceptability.

Population

Study activities will take place in 33 clusters. At each cluster, two study populations will be enrolled and evaluated separately: health workers and patients. To be eligible for participation, **health workers** must be: (a) ≥ 18 years old, (b) working full-time at one of the health facilities included in the study, and (c) involved in Malawi’s HIV program. **Patients** must be: (a) ≥ 15 years old and (b) an index, contact or parent/guardian of an index or contact. Persons that do not meet these criteria will be excluded. We aim to enroll at least 2 health workers per cluster for a minimum of 66 health workers in the study. We will enroll up to 800 patients (600 indexes and 200 contacts) over the study period.

Procedures and implementation interventions

Standard implementation

All facilities participating in the study will receive standard ACT implementation strategies. In Malawi, the standard ACT implementation strategies consist of 1) a brief ACT training, and 2) routine facility support. The brief training is centralized and conducted in-person. It is primarily didactic and provides an overview of ACT procedures and counseling approaches. Tingathe (or other partners) provide routine supervision to all facilities for all supported activities. Routine supervision consists of examining facility performance data, and providing feedback on the overall program. None of these procedures will be altered by the study.

Enhanced implementation

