Analyses: Data from quarters 1 through 4 (the cluster RCT design) will be analyzed using a negative binomial mixed-effects model accounting for quarterly repeated measures within each cluster. Models will use a log link, contain terms for randomization arm, and the natural-log transformed number of potential indexes will be incorporated as an offset term. Key baseline variables of interest, such as district, will be adjusted for. Rate ratios and 95% confidence intervals will be used to estimate the effect sizes and quantify the precision of effect estimates for the main analyses which will compare the enhanced versus standard arms for rates of each service uptake outcome per the total number of potential indexes (5 main endpoints denoted above). Secondary endpoints will take the same approach and use a negative binomial mixed effects model as well. Several secondary endpoints are proportion measures; for those endpoints effect size will be measured using a risk ratio and corresponding 95% confidence interval comparing the enhanced versus standard arms. To assess maintenance, interaction terms between quarters and randomization arm will be included to assess whether effects remain constant, intensify, or diminish over time during quarters 1 through 6.

Statistical power assumption, models, and estimates: Sample size calculations were guided by data from the 33 proposed clusters in the two districts from 2019-2020. In these two districts (Machinga and Balaka), Tingatthe supports 34 MOH facilities with implementation of the national HIV program and supervises approximately 150 community health workers and 100 HIV diagnostic assistants. Two nearby facilities in Balaka will be combined for analysis such that the 34 facilities are handled as 33 clusters.

Across these 33 clusters, 4600 persons are diagnosed with HIV each year and another 49,000 are already taking ART. From this, we estimated 35 new HIV-positive diagnoses per cluster per quarter and 372 ART patients per cluster per quarter or approximately 407 total potential indexes per facility per quarter. On average, of these 407 total potential indexes, there were approximately 86 indexes identified (0.21), 97 contacts elicited (0.24), 12 self-test kits distributed (0.03), 25 contacts tested (0.06), and 3 contacts diagnosed as HIV-positive (0.007). These values informed our assumptions for the standard arm.

Power for primary analyses:

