Aim 3 Analytic methods (Cost-effectiveness)

In Aim 3, we will explore the budget impact and cost-effectiveness of the enhanced and standard approaches. Our modeling will allow us to examine the inherent tradeoffs of the high upfront and ongoing expenditures of the enhanced package with the anticipated future health benefits, such as earlier linkage to care and averted illness that are known to be realized with more effective contact tracing and testing. All analytic decisions will be guided by best practices in implementation economics, a rapidly evolving field.

Cost measurement: We will embed an empirical costing study in our trial. Costs will be collected in two ways: micro-costing and time-motion logs (self-reported and directly observed). Micro-costing will be used to quantify resources associated with the development and implementation of the entire enhanced package. This includes costs of blended learning development, tablets, HIV tests and supplies, travel and telecommunications for tracing, and training expenses. Cost data will be available through contractual information with developers, receipts, and MOH supply chain partners. We will also extract data from project expenditure and management records, including purchase logs and human resources records (e.g. health worker rota), where appropriate. Time-motion assessments in both arms will record staff time and effort on ACT tasks, allowing us to reliably apportion effort expended on ACT activities. This includes health worker and facilitator time spent with the blended learning package and time spent counseling indexes, tracing contacts, and supporting contacts with HIV prevention or treatment services. Data for time-motion logs will be collected by observing staff in each cluster approximately two times. Our research team has conducted these assessments previously. They will be conducted in line with the STAMP checklist (Suggested Time and Motion Procedures).⁹⁰⁻⁹² Additionally, on the provider survey, health care workers will report estimated time spent on these activities.

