We will record this information in structured spreadsheets that document each resource, category, quantity, and unit cost. This comprehensive costing will follow international conventions for costing (i.e. including items for staff, equipment, consumables, and any overhead that are not common to both arms); discounting future costs; and reporting based on accepted practices⁹³ and guidelines from the Panel on Cost-Effectiveness in Health and Medicine.⁹⁴ We will not include any costs related to study-specific activities (e.g. data collection).

We will first conduct a budget impact analysis, comparing total costs associated with the development and implementation of the enhanced implementation strategy to the standard strategy to provide affordability information.⁹⁵⁻⁹⁷ This will be conducted from the perspective of the health-system, evaluating programmatic costs at a per facility basis. We will initially examine only facilities under observation, but ultimately extrapolate the model to 750 sites that make up Malawi's national HIV program.⁹⁸ Due to up-front costs of developing the capacity-building blended learning tool, as the scale and duration of implementation increases and expands, we expect that the cost per facility will decrease.

Cost effectiveness modeling: We will conduct cost-effectiveness analysis, modeling incremental cost effectiveness ratios (ICERs) per contact tested and per HIV-positive patient diagnosed. We may also examine incremental cost per HIV infection averted and per disability adjusted life year (DALY) averted comparing the enhanced to the standard approach. We will construct a hybrid decision-tree/Markov model to reflect the relevant programmatic components and clinical outcomes based on ACT implementation as described above and a literature review of key parameters. This model will first be limited to the trial population, estimating approximately 50,000 total potential index patients in these 33 clusters over one year, and then expanded to the national program—estimating approximately 800,000 potential annual indexes over one, three, and five years. Imbedded Markov models will

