account for the health-state trajectories of HIV-positive and HIV-negative contacts, as well as pediatric and adult contacts. All transition probabilities will be informed by mean observed ACT indicators in the trial (base case) with distribution of upper and lower extremes informed by the highest and lowest performing sites. One-way sensitivity will be conducted with all model parameters individually. Probabilistic uncertainty will be conducted using Latin Hypercube Sampling, varying all parameters simultaneously. Analyses will be performed using Excel and the Excel-based add-on, DecisionTree or comparable software.

Additional exploratory analyses of interest

In addition to the three aims described above, a range of exploratory questions and tertiary analyses may be explored relating different indicators to one another. Some examples include:

- Which health worker, patient, and facility characteristics are associated with selection of each type of contact tracing method?
- Which health worker and facility characteristics are associated with improved fidelity?
- Which facility characteristics are associated with adoption and adherence to the implementation intervention?
- Is adoption of and adherence to the implementation intervention associated with improved service uptake?
- Is health worker fidelity associated with patient acceptability?

Ethical and human subjects considerations

Institutional Review Board oversight and informed consent

Approval for the study will be sought from UNC's IRB and Malawi's National Health Sciences Research Committee. These two bodies will provide oversight for the study. This protocol and the informed consent documents and any subsequent modifications will be reviewed and approved by both bodies. All procedures conform to US and Malawian ethical standards regarding research involving human subjects.

Written informed consent will be obtained on paper or electronically. All study participants will sign an informed consent prior to enrollment in an appropriate language (English or Chichewa). The consent form will describe the purpose of the study, the procedures to be followed, the contact information of the local study contact investigator, and the risks and benefits of participation in accordance with all applicable regulations.

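### Aim 3 takes the spread of the trial-based transition probabilities from the best and worst sites, so on the natural reading the probabilistic analysis would show site-to-site variation and not uncertainty in the arm means

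*Combined protocol and SAP*

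**What the plan says.** In the combined protocol and SAP, under Aim 3 Analytic methods (Cost-effectiveness), the cost-effectiveness paragraphs set out a hybrid decision-tree/Markov model, "modeling incremental cost effectiveness ratios (ICERs) per contact tested and per HIV-positive patient diagnosed". The model covers the 33-cluster trial population first and the national program afterwards.

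The base-case transition probabilities are the mean observed trial indicators, "with distribution of upper and lower extremes informed by the highest and lowest performing sites". Two sensitivity analyses follow: a one-way analysis of every parameter, then "Probabilistic uncertainty will be conducted using Latin Hypercube Sampling, varying all parameters simultaneously".

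Aim 3 mentions no standard error, confidence interval, fitted distribution or bootstrap for these probabilities. It does not say whether the extremes are limits or percentiles, whether they are taken within arm or over all clusters, what shape is assumed, or whether the enhanced and standard draws are linked.

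Aim 2 does plan measures of precision: "Rate ratios and 95% confidence intervals will be used to estimate the effect sizes and quantify the precision of effect estimates". Nothing in Aim 3 carries them into the model.

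**The concern.** An ICER comparing the enhanced with the standard package for a pooled population depends on each arm's mean performance. A probabilistic analysis should show how well the trial has determined those means. The gap between the best and worst site measures something else: real differences between sites plus chance variation within sites. It tends to widen as sites are added, whereas uncertainty about a mean shrinks. The standard arm, with 22 clusters and the better-determined mean, would receive the more distorted spread.

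The arm difference in contacts tested, or in HIV-positive contacts diagnosed, is the denominator of the two ICERs that the plan names. If its sampled spread is wrong, so is the share of draws in which the denominator is near or below zero, where an ICER is unstable or changes sign. The Protocol Summary ranks this output highly: "Three sets of primary outcomes will be compared between the standard and enhanced arm: implementation outcomes, service uptake outcomes, and cost-effectiveness outcomes".

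**Working it through.** **Inputs.** From the primary power table in Aim 2, for contacts tested: rates per potential index 0.1247 (enhanced) and 0.0614 (standard), rate ratio 2.03, random intercept variance 0.3340, negative binomial scale 0.2847, stated power 85%. Also from the plan: 407 potential indexes per cluster-quarter, 11 and 22 clusters, four quarters, alpha 0.05 (taken as two-sided).

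**Step 1: do these values reproduce the plan's own power?** The variance of a cluster's log rate over four quarters is v = RIV + (1/(407 × rate) + scale)/4.

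- Enhanced: 0.3340 + (1/50.75 + 0.2847)/4 = 0.410
- Standard: 0.3340 + (1/24.99 + 0.2847)/4 = 0.415
- SE(log RR) = √(0.410/11 + 0.415/22) = 0.237
- Power = Φ(ln(2.03)/0.237 − 1.96) = 84.8%, against 85% stated

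The planning values are therefore a fair basis for illustration.

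**Step 2: a site range against the uncertainty of a mean.** For normally distributed site values, in units of the between-site SD:

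| | 11 sites | 22 sites |
|---|---|---|
| Expected range, lowest to highest | 3.17 | 3.82 |
| 95% CI width of the mean, 2 × 1.96/√n | 1.18 | 0.84 |

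The two quantities move in opposite directions as n grows.

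The same holds for contacts tested simulated from the plan's values. The typical site extremes are about 0.044 to 0.32 in the enhanced arm, against a t-based 95% CI half-width of about 0.059 for the arm mean. In the standard arm they are about 0.017 to 0.195, against 0.021. The range is about 2.4 and 4.4 times the full CI width.

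**Step 3: effect on the sampled arm difference.** Trials were simulated from the same values, with a log-normal cluster effect and negative binomial quarterly counts. In each trial the within-arm lowest and highest site rates served as limits, with three assumed shapes and several assumed links between the arms (Gaussian copula for partial correlation). The resulting 95% interval for the arm difference was compared with a cluster bootstrap by arm. Median width ratios:

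| Link between arm draws | PERT | Triangular | Uniform |
|---|---|---|---|
| Independent | 2.3 | 2.6 | 3.5 |
| Correlation 0.5 | 1.8 | 2.0 | 2.7 |
| Correlation 0.8 | 1.3 | 1.4 | 2.0 |
| Fully linked (same quantile) | 0.7 | 0.9 | 1.0 |

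Repeat runs agree to about 0.1.

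With independent draws, the median share of draws favouring the enhanced arm is about 88% / 86% / 77%, against 99.8% for the bootstrap. The lower 95% limit is at or below zero in about 90% / 90% / 99% of simulated trials, against about 19%. At correlation 0.8 that frequency falls to about 29% / 39% / 67%. When fully linked it is about 9% / 13% / 16%, slightly below the bootstrap.

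For HIV-positive contacts with independent draws, the width ratios are again 2.3 / 2.6 / 3.5.

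**The case against.** Three objections have weight.

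**The text does not expressly tie the sampling to the site extremes.** The Latin Hypercube sentence is separate, "informed by" is loose wording, and high and low limits suit the one-way analysis that is named in between. This stands as a limit on the claim: a reader might infer that the plan mandates site-range sampling, and it does not say so. But the site extremes are described as the source of the distribution, all parameters are then varied, and no alternative is offered, so this remains the natural reading. The general commitment, "All analytic decisions will be guided by best practices in implementation economics, a rapidly evolving field", does not replace a specific rule.

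**The direction is not fixed.** A reader might infer that the plan necessarily overstates uncertainty. That goes too far. Independent draws are the usual default and do overstate it, as do partly correlated draws at the levels checked. With fully linked arms, however, the same rule gives an interval about as wide as the bootstrap or somewhat narrower. The plan says nothing about linkage.

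**Little formally turns on it.** Aim 3 states no threshold, test or decision rule, describes its purpose as exploring cost-effectiveness, and commits to recognised costing and reporting guidance. The main Study design and outcomes section also drops the word primary. This limits the consequence but does not make the intervals right.

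It can also be said that site variation matters when the plan will "ultimately extrapolate the model to 750 sites". It does, as a question about how performance may differ between places. An aggregate national ICER still depends on mean performance, so site variation belongs in a labelled scenario.

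**Conclusion.** The concern holds in conditional form. If the probabilistic analysis uses the only spread that Aim 3 gives, it will reflect differences between sites and not sampling uncertainty in the arm means, and its intervals will be misstated.

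For contacts tested, the interval for the arm difference could be anywhere from about 0.7 to 3.5 times the bootstrap width from the same trial data, depending on shape and linkage. It is overstated under independent or partly correlated draws and may be understated if the arms are fully linked.

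These figures rest on the Aim 2 planning values, equal mean volume across clusters, within-arm extremes used as limits, and shapes and links that the plan does not specify. They concern only the trial-based probabilities.

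The documents do not support the further inference that the ICER intervals will be wrong by these factors or the economic conclusion inconclusive: the spread of the cost and literature inputs is not given, so the full ICER interval cannot be computed. Base-case ICERs and all Aim 2 results are unaffected. The point should be settled before results are known, because it can change how certain the economic result appears.

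**What to change.** State in Aim 3 that, in the probabilistic analysis, trial-derived probabilities will be drawn in one of two ways:

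- from the cluster-adjusted sampling distributions of the Aim 2 main and cascade estimates (arm rates and rate or risk ratios, with their covariance); or
- from a cluster bootstrap by arm that keeps the cascade steps of each cluster together.

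Either choice also settles how the arms are linked. Reserve highest- and lowest-site values for the one-way analyses and for a labelled site-performance scenario, which keeps site variation in view for the national extrapolation. Add a table giving each parameter's distribution and source.

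The cost is a wording change, the table and a little extra analysis. Most inputs come from models already planned in Aim 2, and the draws can be imported into the Excel model that Aim 3 names. No data collection, sample size or Aim 2 analysis changes.
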